Social support messages are an important part of close relationships (Cutrona & Suhr, 1992); however, recipients perceive some supportive messages to be unhelpful or unwanted (Floyd & Ray, 2017). In general, emotional support messages are viewed as a particularly useful form of support in the months following a cancer diagnosis (Arora et al., 2007). There are instances, though, of cancer patients viewing some emotional support messages negatively (Ray & Veluscek, 2017, 2018). Much of the prior research looking at peoples' reactions to emotional support messages have done so by looking for differences between high, moderate, and low-quality messages (High & Dillard, 2012), and have not considered the possibility that some offers of emotional support may contain both positive statements of empathy and caring and also negative statements of criticism and blame. Therefore, the present study investigates how cancer patients rate emotional support messages that consist of different percentages of positive and negative statements. Additionally, prior research has shown that some messages may be retained in memory for years after they are communicated (Knapp, Stohl, & Reardon, 1981), and some of these memorable messages can be classified as supportive messages (Wang, 2012). However, minimal research has focused on what is specifically remembered from supportive messages, particularly if those messages are composed of both positive and negative statements. Research by Ray and Veluscek (2017) has shown, though, that cancer patients can readily recall both positive and negative support messages received in the year after initial diagnosis and that receiving negative messages sometimes led to re-evaluating whether future updates would be shared with the supporter. Furthermore, the well-supported propensity for humans to pay greater attention and give more processing to negative information than positive information (Baumeister, 2001), would suggest that negative portions of ambivalent support messages would have a stronger influence on the recipient, particularly in terms of what is recalled (Bless, Hamilton, & Mackie, 1992; Finkenauer & Rimé, 1998). The present study tests this negativity bias and the findings will illuminate how cancer patients process, perceive, and recall emotional support messages that have both positive and negative components. To test the possible effects of negative portions of messages, 18 message conditions have been developed (see list provided under Participation heading). This results in a nested factorial design in which you have 5

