
message conditions (0, 20, 40, 60, or 80 percent negativity), 2 conditions based on the placement of the negative portions (beginning or end), and 2 versions of each message condition to allow for the messages to be analyzed as random factors. A 5x2x2 design typically yields 20 cells; however, when there is 0% negative portions of a message, it is unnecessary to consider the placement of the negative portions that do not exist. This results in 18 conditions as opposed to 20 conditions.

Study Purpose/Objective

To understand how cancer patients react to and recall emotional support messages that contain different percentages of positive statements of empathy and caring and also negative statements of criticism and blame.

Study Aims

Aim #1: To determine how cancer patients rate emotional support messages that consist of differing percentages of negative statements (0, 20, 40, 60, or 80 percent) and messages in which those negative portions occur at either the beginning or end of the supportive message.

Aim #2: To determine what portions of emotional support messages that consist of differing percentages of negative and positive statements cancer patients recall in the minutes after reading a message, and whether the placement of the negative portions at either the beginning or end of the message also affects recall.

Hypotheses & Research Questions

Hypotheses 1-4 and Research Questions 1-4 address Study Aim #1.

H1: Cancer patients' ratings of message effectiveness differ based on the percentage of the support message that is negative.

RQ1: How, if at all, do cancer patients' ratings of message effectiveness differ depending on whether negative portions of messages occur at the beginning or end of the entire message?

H2: Cancer patients' ratings of supporter competence differ based on the percentage of the support message that is negative.

RQ2: How, if at all, do cancer patients' ratings of supporter competence differ depending on whether negative portions of messages occur at the beginning or end of the entire message?

H3: Cancer patients' likelihood of seeking support from a supporter in the future differs based on the percentage of the support message that is negative.

RQ3: How, if at all, do cancer patients' likelihood of seeking support from a supporter in the future differ depending on whether negative portions of messages occur at the beginning or end of the entire message?

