H4: Cancer patients' self-reports of emotional improvement after receiving a support message differs based on the percentage of the support message that is negative.

RQ4: How, if at all, do cancer patients' self-reports of emotional improvement after receiving a support message differ depending on whether negative portions of messages occur at the beginning or end of the entire message?

Hypotheses 5-7 address Study Aim #2.

H5: Cancer patients recall negative portions of supportive messages more frequently than they recall positive portions of supportive messages.

H6: As the percentage of negative portions of a supportive message increases, cancer patients likelihood to recall negative portions of supportive messages also increases.

H7: The number of negative words recalled from the supportive messages by cancer patients differ depending on the percentage of the message that is negative.

Methods

This is a cross-sectional, observational survey study. Data will be collected through a mass email disseminated through the online survey platform Qualtrics.

Recruitment and Eligibility

800 participants will be recruited from Moffitt TCC-consented patients who have agreed to be contacted for future research.

Inclusion Criteria: Living patients, 18 years of age or older, diagnosis of breast, prostate, thoracic, or digestive cancer in the past 3 years, consent to the Moffitt TCC protocol and indication of their willingness to be contacted for future research by including an email contact, and ability to read and write fluently in English.

A random selection of at least 800 patients who fit inclusion criteria will be drawn by Moffitt Collaborative Data Services. An invitation to participate in the current study will be sent to participants via an email disseminated through the online survey host Qualtrics. The contact list of email recipients will be uploaded into the Qualtrics system and the email will be sent from [name] (study team member). If a potential participant were to choose to reply to this email with questions about the study or for any other reason, these replies would be sent to [name], who would be tasked with responding to the potential participant's message. The invitation will include a description of the study and a link to the study survey.

Consent Process

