Because participation will occur solely online and consists only of an online questionnaire, the research team requests a waiver for written consent. Instead, we request that consent can be given by having participants read an informed consent statement on the opening page of the online questionnaire. Clicking to the next page and beginning survey would signify consenting to participate.

Participation

Participating in the study consists of taking an online questionnaire. The questionnaire begins with self-reported demographic questions (biological sex, age, ethnicity, time since initial cancer diagnosis, cancer site). Next, the participant is asked to think of someone they know well but who they did not directly disclose the news of their cancer diagnosis. Then, the participant is told to imagine receiving a written message of support from this person in the days after initially being diagnosed with cancer. The participant then reads one of 18 different emotional support messages randomly assigned through the Qualtrics survey system. These 18 messages are each 100 words long and systematically vary in how much of the message is composed of negative statements of criticism and positive statements of caring. The 18 message conditions are part of a 5x2x2 nested factorial design and are as follows:

- Two messages composed of only positive statements (0% negative).
- Two messages in which the last 20% of the message consists of negative statements of criticism.
- Two message in which the first 20% of the message consists of negative statements of criticism.
- Two messages in which the last 40% of the message consists of negative statements of criticism.
- Two message in which the first 40% of the message consists of negative statements of criticism.
- Two messages in which the last 60% of the message consists of negative statements of criticism.
- Two message in which the first 60% of the message consists of negative statements of criticism.
- Two messages in which the last 80% of the message consists of negative statements of criticism.
- Two message in which the first 80% of the message consists of negative statements of criticism.

The participants then answer a series of closed ended scales regarding quality of the support message, the supporter's competence, the amount of emotional improvement they experienced after reading the message, and the likelihood to seek support from the person they chose earlier

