Statistical analyses will consist of 5x2x2 nested factorial ANOVA models. The first study aim will be tested through 4 ANOVA models that will test for differences between participants who received the different messages in terms of 1) perceived message effectiveness, 2) perceptions of supporter competence, 3) likelihood to seek support from the supporter in the future, and 4) self-reports of emotional improvement. Depending on the correlations among the dependent variables, a MANOVA may be used instead of an ANOVA to test the first aim of the study. Similarly, if significant covariates (such as age or times since diagnosis) are found, the ANOVA/MANOVA could become an ANCOVA or MANCOVA. To test the second aim of the study, a chi-square analysis will test to see if participants recall negative portions of messages more frequently than positive portions of messages depending on which message they received (i.e., dependent on the position and percentage of the negative message portions). The second aim will also be tested using ANOVA models to determine if significant differences occurred in the number of negative words that were recalled across the 18 messages received (i.e., dependent on the position and percentage of the negative message portions). The software program LIWC (Linguistic Inquiry and Word Count) will be used determine the number of negative words recalled by the participants in their open-ended responses.

Potential Benefits

There are no benefits for being in this study; however, by joining this research study, the participant is helping to provide information which may help science and society.

Potential Risks

Because of the personal nature of the questions to be asked, the participant might reflect on unpleasant memories while completing the questionnaire. Although not expected to occur, it is

possible that a breach of confidentiality could occur if the computer on which the data file is stored is compromised or otherwise hacked or illegally accessed.

Compensation, Benefits, and Risks

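### The only planned recall-frequency test (a chi-square by message) does not isolate H5; H5 needs its own within-participant test on the 16 mixed messages, adjusted for words available

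*Combined protocol and SAP*

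**What the plan says.** The background section states the purpose: "The present study tests this negativity bias". It frames the expectation for messages that mix both kinds of statement: "negative portions of ambivalent support messages would have a stronger influence on the recipient, particularly in terms of what is recalled".

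Hypotheses & Research Questions then separates two claims about recall frequency:
- H5 is a contrast between two kinds of text: "Cancer patients recall negative portions of supportive messages more frequently than they recall positive portions of supportive messages".
- H6 is a dose relation: "As the percentage of negative portions of a supportive message increases, cancer patients likelihood to recall negative portions of supportive messages also increases".

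Aim #2 adds a further question: "whether the placement of the negative portions at either the beginning or end of the message also affects recall".

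For recall frequency, Planned Analyses gives a single test, which borrows H5's comparison: "a chi-square analysis will test to see if participants recall negative portions of messages more frequently than positive portions of messages". The sentence continues: "depending on which message they received (i.e., dependent on the position and percentage of the negative message portions". It states no table layout, unit of analysis or expected counts. The other Aim #2 analysis is a set of ANOVA models on the number of negative words recalled. It has no positive comparator, so it cannot stand in for H5.

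Under Participation, each person reads one of 18 messages of 100 words. Two messages contain no negative text. The other 16 are 20%, 40%, 60% or 80% negative, with four messages at each level.

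**The concern.** H5 asks whether one kind of text is recalled more than the other. A test across messages asks whether recall differs from message to message. Because the messages were built to contain between 20 and 80 negative words, recall of negative text should differ between them even if every phrase is equally memorable. A significant chi-square would then reflect the design and say nothing about bias.

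H5 is the direct test of the negativity bias that the study sets out to examine. If the by-message result were taken as the answer to H5, a design artefact could be reported as evidence for it. If the chi-square was meant for H6, H5 has no stated test. It also fits H6 loosely: H6 predicts an increase, whereas an ordinary chi-square responds to any difference, including one due to position alone.

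**Working it through.** **The plan's own figure.** With 18 groups, f = 0.25 and alpha = 0.05, the noncentrality at N = 479 is 479 × 0.0625 = 29.9 on 17 and 461 df, and power is 0.950. So 479 reproduces. It sizes the 18-group F test and no recall contrast. The documents give no recall rates, so everything below rests on stated assumptions.

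**Text available.** Negative words over the mixed messages: 4 × (20 + 40 + 60 + 80) = 800 of 1,600, or 50%. With equal completion, positive and negative text are balanced over these 16. Participants on them: 479 × 16/18 = 425.8.

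**By-message reading, one recalled unit per person.** With no bias, the chance that the unit is negative equals the text share x: 0.2, 0.4, 0.6, 0.8.
- Mean 0.5; variance (0.09 + 0.01 + 0.01 + 0.09)/4 = 0.05.
- Noncentrality 425.8 × 0.05/0.25 = 85.2 on 15 df; power above 0.9999.
- With positive text weighted three times (H5 reversed), P = (x/3)/(x/3 + 1 − x) = 0.077, 0.182, 0.333, 0.571, mean 0.291. The noncentrality is about 71, and the test again rejects in about 100%.

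**By-message reading, any negative portion recalled (yes/no).** Example: 10 phrases, each recalled with probability 0.15, no bias. P(any negative) = 1 − 0.85^k for k = 2, 4, 6, 8, which gives 0.28, 0.48, 0.62, 0.73. Recall climbs with the amount of text alone.

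I simulated 18 settings: 5, 10 or 20 phrases; mean phrase recall 5%, 15% or 30%; between-person logit SD 0 or 1. Tests are two-sided at 0.05.

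| 16 mixed messages, N about 479 | Chi-square rejects |
|---|---|
| No bias | about 40% to 100%, median about 97% |
| Negative phrases recalled at half the positive rate | about 20% to 100%, median 88% to 94% in repeat runs |

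**Within-message reading.** A reader of a mixed message can recall both kinds of text. Counting negative and positive recalls in an ordinary chi-square enters that person twice as if independent. The size of the resulting error depends on a within-person correlation that the documents do not give.

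**The 0% messages.** Negative recall is impossible there, and no exclusion is stated under either reading.

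**Fit to H6 (16 messages, N = 479).**
- Position effect only (45% first, 65% last): noncentrality 425.8 × 0.01/0.2475 = 17.2 on 15 df, power 75% (simulated 74%). A trend test on percent negative rejects in 4.5%.
- True linear rise from 50% to 70%: noncentrality 425.8 × 0.00556/0.24 = 9.9. Power is 45% on 15 df (simulated 44%), against 88% on 1 df for a trend (simulated 89%).

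**Candidate replacement.** McNemar's test on the 16 mixed messages rejects in 2% to 5% with no bias, but only under two conditions:
- *Messages equally memorable.* With an assumed message-level logit SD of 0.25, separate for negative and positive text, no-bias rejection rises to a median of about 8%. At 0.5 it is about 20%.
- *Balanced completion.* If relative completion falls 100/90/80/70% as percent negative rises, available text is (20 + 36 + 48 + 56)/340 = 47% negative. McNemar then rejects in 8% to 29% (median 18%) with no bias.

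**The case against.** The strongest reply is that Planned Analyses never fixes the table. The sentence could mean a negative-versus-positive comparison within each message or percentage level, or a fit against the design shares, and either would bear on H5. That stands: the plan is underspecified, and it cannot be said that the test certainly ignores H5. It does not remove the problem, because an ordinary chi-square on such counts would still ignore pairing, and no adjustment for text share is stated.

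Four stronger readings are tempting, and the documents do not support them.
- *That the chi-square always rejects, whatever the bias.* The near-100% figures belong to one recalled unit per person. Participation asks for phrases or sentences in the plural, and under any-negative coding rejection is usual but not universal.
- *That it would miss a true H5.* If negative recall were constant at 60% in every mixed message, the chi-square would reject in only about 5%. But relative to text share, that needs negative text weighted 6.0, 2.25, 1.0 and 0.375 times at 20%, 40%, 60% and 80% negative, which is a reversed bias at the top level. This is a special case that uses a different definition of H5.
- *That pooling all 18 messages biases the result towards positive text.* Negative text would be 800 of 1,800 words (44.4%), but the plan does not state a pooled test.
- *That a false confirmation will be reported.* The plan does not say that an omnibus rejection will be read as H5 without regard to direction. The risk is real, but it is not a stated intention.

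Appendices A and B were not in the text supplied. They are described as the questionnaire and the messages, so a scoring rule may exist there and its absence is not held against the plan.

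**Conclusion.** The concern holds and should be fixed before analysis. H5 is a negative-versus-positive contrast. The only recall-frequency test is conditioned on message, and its layout is not given. On the by-message reading, it responds mainly to the designed amount of negative text and does not identify H5. On the within-message reading, it ignores pairing. Neither reading deals with the 0% messages.

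The direction of the problem is firm because it follows from the 20% to 80% design. The exact rejection rates are not: they rest on assumed phrase counts, recall probabilities and near-equal allocation. The confident claim is that the stated analysis would not answer the stated hypothesis. It is not established that the planned test must give a wrong answer.

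**What to change.** State a separate test for H5:
- Restrict it to the 16 mixed messages, and report the 0% messages separately.
- For each participant, score negative and positive recall under a written rule.
- Make the primary analysis a model of negative versus positive recall that accounts for words available, for example a log-link count model with a log(words available) offset and participant clustering.
- Include a message random effect, in line with the plan's stated reason for writing two versions of each message (so that messages can be treated as random). Let it differ between negative and positive text, because an effect common to both cancels out of the contrast.
- Keep McNemar's test as a sensitivity analysis. Making the offset model primary from the start avoids choosing between the two after looking at completion.

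For H6, test the increase directly with a slope or trend on percent negative, and enter position as a separate term, which also answers Aim #2's placement question.

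Cost: no change to data collection and slightly more analysis work. About 11% of participants (479 × 2/18 = 53, or 800 × 2/18 = 89) leave the H5 test, and they carry no information on it. The message term will widen the interval somewhat.

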in the survey in the future. Participants also answer an open-ended question in which they are asked what specific phrases or sentences they recall from the support message they read.

During pilot tests of the questionnaire, the average time to complete was 7.5 minutes. Three weekly reminders will be sent by email to those who have not completed the survey to encourage participation. Those who opt out will not be contacted with follow-up emails. The recruitment emails will include a link that can be clicked to opt out of the recruitment process for the study.

See Appendix A for the questionnaire and Appendix B for the message conditions.

Planned Analyses

The number of participants was determined through power analyses performed by the statistical software program G*POWER. The suggested sample size provided by G*POWER was 479. Specifically, this was determined by conducting an *a priori* analysis with an effect size (f) of .25, alpha error probability of .05, power ($1 - \beta$ error probability) of .95, and 18 groups, which is the total number of message conditions listed above. Importantly, a power analysis using these same parameters but for an ANCOVA also yielded a suggested samples size of 479.

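### No stated analysis tests the order and direction that H6 claims; the plan needs a specific slope test over the messages that contain a negative portion

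*Combined protocol and SAP*

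**What the plan says.** H6, under Hypotheses & Research Questions, is ordered and directional: "As the percentage of negative portions of a supportive message increases, cancer patients likelihood to recall negative portions of supportive messages also increases". H7, next to it, claims only that word counts differ. The levels have a natural numeric order; the design paragraph before Study Purpose/Objective lists "message conditions (0, 20, 40, 60, or 80 percent negativity), 2 conditions based on the placement of the negative portions".

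For the second aim, Planned Analyses gives two analyses:

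- A chi-square on recall frequency: "a chi-square analysis will test to see if participants recall negative portions of messages more frequently than positive portions of messages". The plan ties this comparison to the message that each person read, by placement as well as percentage.
- ANOVA models on negative-word counts, which ask "if significant differences occurred in the number of negative words that were recalled across the 18 messages received". This is H7.

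The section names no trend test, ordered contrast, percentage scores or direction, and gives no rule for when H6 counts as supported. It does not say whether the chi-square table has rows for percentages, for percentage by placement, or for single messages, and it does not exclude the 0% messages. The only power calculation is for an 18-group ANOVA.

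**The concern.** H6 says that one quantity rises as another rises. An ordinary Pearson chi-square asks only whether proportions differ between groups, in any pattern. Two things follow if it is used to judge H6.

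- A significant result does not establish an increase. Falling recall, or recall that peaks in the middle, also produces one. The 0% messages make this worse: they have no negative portion to recall, so they differ from the rest by construction.
- A non-significant result is hard to read, because the test spreads its sensitivity over patterns that H6 does not predict.

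At stake is whether the report can state, on a rule fixed in advance, that H6 was or was not supported.

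**Working it through.** **Inputs from the protocol.** 18 messages, with random assignment (Participation). Alpha .05, f = .25, power .95, N = 479 (Planned Analyses). Recruitment figure 800 (Recruitment and Eligibility). Five prizes at odds of about 1 in 120 (Compensation, Benefits, and Risks) imply about 5 × 120 = 600 respondents.

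**Assumptions.** Equal allocation, so each percentage from 20 to 80 has 4 of the 18 messages and the 0% level has 2. The protocol gives no recall rates; all rates below are illustrative.

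**The plan's own figure.** One-way ANOVA, noncentral F with λ = f²N, 17 and N − 18 df. At N = 479, λ = 0.0625 × 479 = 29.94 and power is .9502; at 478 it is .9496. The 479 reproduces, but it does not concern recall frequency.

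**Pearson noncentrality for the messages with a negative portion.** λ = n Σ(pᵢ − p̄)² / [p̄(1 − p̄)], where n is the number per percentage level. At N = 479, n = 479 × 4/18 = 106.4. The degrees of freedom are 3 (four percentages), 7 (percentage by placement) or 15 (16 messages). If the rise is exactly linear, the 1-df trend test has the same λ.

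**1. Patterns that contradict H6, N = 479.**

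- Rise then fall, 65/80/80/65%: p̄ = .725, Σ = 4 × .075² = .0225, λ = 106.4 × .0225 / .1994 = 12.0. Pearson power is 84% (3 df) or 55% (15 df). An upward trend is declared about 3% of the time.
- Steady fall from 70% to 50%: p̄ = .60, Σ = .0222, λ = 106.4 × .0222 / .24 = 9.9. Pearson power is 75% (3 df) or 45% (15 df). An upward trend is essentially never declared.

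**2. The 0% messages left in.** Assume 2% are coded as recalling something negative there. The 0% level has 479 × 2/18 = 53.2 people.

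- Falling recall, 70/60/50/40% over the 20–80% messages: λ = 74.5, so 4-df Pearson power exceeds 99.9%.
- Flat 60% over the 20–80% messages: p̄ = (2 + 8 × 60)/9 = 53.6%, λ = 64.0. Pearson again rejects almost always. A linear trend test that includes the 0% level has an expected z of 4.8, although recall does not change from 20% to 80%. A trend test alone is therefore not enough; the 0% messages must be excluded.

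**3. Power when recall rises linearly.** A two-sided 1-df test has 80% power at λ = 7.85. Pearson power at the same λ, whatever the recall rates:

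| df | Layout | Power |
|---|---|---|
| 3 | four percentages | 64% |
| 4 | five percentages | 60% |
| 7 | percentage by placement, no 0% | 49% |
| 15 | 16 messages | 35% |
| 17 | 18 messages | 33% |

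For an assumed 50/56/62/68%: p̄ = .59, Σ = 2(.09² + .03²) = .018, and at N = 479 λ = 106.4 × .018 / .2419 = 7.92.

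| N | Pooled trend | Pearson, 3 df | Pearson, 15 df |
|---|---|---|---|
| 479 | 80% | 65% | 36% |
| 600 | 88% | 76% | 46% |
| 800 | 95% | 88% | 61% |

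**4. Effect of treating messages as random.** The trend figures above pool people over messages. In a simulation for the same pattern at N = 479, the 16 message proportions were regressed on percentage and placement (16 − 3 = 13 residual df). Power for an upward slope was about 75% with no variation between messages. It was about 65%, 55% and 37% with an assumed between-message SD of 0.2, 0.3 and 0.5 on the logit scale.

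**The case against.** The strongest reply is that the chi-square was never assigned to H6. It compares negative with positive recall, which is H5, and no hypothesis is named. This stands. A reader might infer that the plan gives H6 the wrong test, which should then be replaced or demoted to description. The documents do not support that, and doing so could remove the only test of H5. The extension "dependent on the position and percentage of the negative message portions" may be meant to reach H6. If it is not, H6 has no test at all, and the same addition is needed.

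Second, a chi-square analysis could include a 1-df trend version. The text does not exclude it, but does not say it either.

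Third, a reader might infer that the plan gives up much of its power for H6. That depends on N, layout and assumed rates. By percentage at N = 800, the loss in the example is about 95 − 88 = 7 points, although 800 may count invitations rather than completed surveys. Nor do the pooled trend figures show what a random-message model would achieve; section 4 of the working shows that it can be well below 80%. The Pearson figures also ignore message variation. Power is not the main reason for the change.

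Fourth, proportions would ordinarily be reported beside the test, so a fall or zig-zag would be visible. That is likely, but inspection after an omnibus test is not a pre-specified rule for claiming an increase.

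**Conclusion.** The point holds as a gap: no stated analysis tests H6's order and direction. That follows from the text and needs no assumed rate. If the chi-square is an ordinary Pearson test and is used for H6, it can be significant for patterns that contradict H6 (84% and 75% by percentage in the two examples at N = 479). It is nearly certain to be significant with the 0% messages included. These sizes rest on assumed recall rates and equal allocation.

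The power difference should be given as a range. Where a pooled trend test has 80%, Pearson has about 64% with four percentages and 35% with 16 messages. In the 50/56/62/68% example, pooled trend versus Pearson by percentage is 80% against 65% at N = 479 and 95% against 88% at N = 800, without a random message effect.

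A reader might also take a positive slope as proof that negative content is inherently more memorable. It would match H6 as worded, but every message is 100 words long, so an 80% message offers 80/20 = 4 times as much negative text as a 20% message. Amount of text alone could produce the slope.

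**What to change.** Keep the chi-square, assign it to H5 by name and state its table layout. Add a separate analysis for H6:

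- Define the outcome as whether the participant recalled a negative portion (yes/no), with the coding rule for the open-ended answers.
- Restrict it to the 16 messages that contain a negative portion.
- Fit a logistic model with percentage as a numeric score (20, 40, 60, 80), placement as a factor and message as a random effect. The last follows the protocol's stated intention to analyse messages as random factors.
- Count H6 as supported only if the percentage slope is positive and significant at two-sided alpha .05.
- State that a positive slope may partly reflect the larger amount of negative text at higher percentages.

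The cost is a few sentences in Planned Analyses; no new data are needed. There are two downsides. The slope test is less sensitive to non-monotone patterns, which H6 does not predict. Its power is also below that of a pooled trend test if messages vary. The gain is a test that answers H6.
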